MM - PD, lab and genetic assessments												
Bone marrow 10mL aspirate												
50ml blood sample DIFFUSE LARGE B-CELL LYMPHOMA PATIENTS:												
DLBCL specific assessments												
FDG PET/CT ¹												
Bone marrow aspirate and biopsy [for histological	1									l		l
evaluation of DLBCL involvement]	1	1	1	1				1			1	
DLBCL - PD, lab and genetic assessments												
Tumour sample (where accessbile)												
50ml blood sample	1									l		l

	-		EXPANS	SION STA								
	Week 1					YCLE 3 4						1
	Week 1 Day 1 Dose 1	Week 1 Day 3 Dose 2	Week 1 Day 5 Dose 3	Week 2 Day 1 Dose 4	Week 2 Day 3 Dose 5	Day 5 Dose 6	Week 3 Day 1 Dose 7	Week 3 Day 3 Dose 8	Week 3 Day 5 Dose 9	Week 4 Day 1 Dose	Veek 4 Day 3 Dose	Week 4 Day 5 Dose
Initial tests												
Written informed consent						L						
Medical history												
Disease specific history (MM/DLBCL)												
Adverse Events	×	×	×	×	×	×	×	×	×	×	×	×
Concomitant medications	×	×	×	×	×	×	×	×	×	×	×	×
Physical examination (as per local clinical standards and as considered adequate by the PI)												
Height												
Weight	×-			×-			×-			×-		
Blood pressure	ו			ו			×			ו		
Pulse rate	ו			×			×			ו		
Respiratory Rate												
12-lead ECG	ו			×			ו			ו		
Urinalsyis	×											
Calculated creatinine clearance	L	L	L		L	l			l		I	l
Pregnancy serum (where appropriate) ⁱ	×											
PT and APTT (coagulation testing)												
Full Blood Count (Haematology)												
Haemoglobin	×											
Hematocrit	×											
WBC count with complete manual or automated differential	X			L		l	l	l	l	l	 	l
RBC count	×	l		L	L	l	l	l	l	l	 	l
Platelet count	×											
Biochemistry assessment												
Renal Profile (Sodium, Potassium, Creatinine, Urea, eGFR, blood urea nitrogen) Calcium (bone profile)	××											
Uric acid	×			l			l	l	l	l		
Lactate dehydrogenase	x					-						-
Chloride	x					 						
Bicarbonate	Ŷ			 		 	l	l	 		 	 
Glucose	×										1	
Globulin, AST)	×											
Phosphorous	×											
DTP3												
IMP administration	×	×	×	×	×	×	×	×	×	×	×	×
РК												
4ml blood sample												
MULTIPLE MYELOMA PATIENTS:												
MM specific assessments												
Serum protein electrophoresis (SPEP)	×											
Paraprotein quantification	×											
Serum immunofixation												
Serum immunoglobulin levels												
Serum free light chains (sFLC)	×											
24-hour urine sample for urine proteins and urine immunofixation ^f	×											
FDG-PET/CT whole body MRI, or whole body low-dose												
CT (unless performed within 8 weeks of treatment starting)												
Bone marrow aspirate and biopsy for local determination												
of plasma cell count												
Beta-2 microglobulin level						L	L	L				
MM - PD, lab and genetic assessments												
Bone marrow 10mL aspirate		l										
SOmi blood sample DIFFUSE LARGE B-CELL LYMPHOMA PATIENTS:												
DLBCL specific assessments												
FDG PET/CT	×i											
Bone marrow aspirate and biopsy [for histological	1											1
evaluation of DLBCL involvement] *	1	1	1		1	1			1		1	1
DLBCL - PD, lab and genetic assessments												
Tumour sample (where accessbile) 50ml blood sample												

End of Treatment Visit	-
	End of Study Vis
Initial tests	
Survival Status	X ^k
Written informed consent	
Medical history	
Disease specific history (MM/DLBCL)	
ECOG Performance Status	х
Adverse Events	х
Concomitant medications	х
Physical examination- including ECOG performance status (as per local	
clinical standards and as considered adequate by the PI)	Х
Height and weight	
Blood pressure	х
Pulse rate	х
Respiratory Rate	
12-lead ECG	х
Urinalsyis	
Calculated creatinine clearance	
Pregnancy serum (where appropriate) ⁱ	Х
PT and APTT (coagulation testing)	
Full Blood Count (Haematology)	
Haemoglobin	
Hematocrit	
WBC count with complete manual or automated differential	
RBC count	
Platelet count	
Biochemistry assessment	
Renal Profile (Sodium, Potassium, Creatinine, Urea, eGFR, blood urea nitrogen)	3
Calcium (bone profile)	
Uric acid	
Lactate dehydrogenase	
Chloride	
Bicarbonate	
Glucose	
LFT (ALT, ALP, Total Bilirubin, Albumin, Total protein, Globulin, AST)	
Phosphorous	
PK	
4ml blood sample	
MULTIPLE MYELOMA PATIENTS:	
MM specific assessments	
Serum protein electrophoresis (SPEP)	
Paraprotein quantification	
Serum immunoglobulin levels	
Serum free light chains (sFLC)	1
Plasmacytoma evaluation	
Beta-2 microglobulin level	1

	Maria
	Keys Hospitalised patients will undergo the following sampling: pre-infusion, 5min, 0.25hr,
	0.5hrs, 1hr, 2hr, 4hr, 8hr, 12hr, 16hr, and 24hr
	Non-hospitalised patients will undergo the following sampling: pre-infusion, 5min,
	0.25hr, 0.5hrs, 1hr, 2hr and 4hr (post-infusion) For PK samples taken during the first hour
а	of sampling, these samples need to be taken as precisely as possible at the specified time
	points idealy within +/- 2 minutes. For samples taken after the first hour, there can be a
	small window of +/- 5 minutes, for samples taken at 12 hours and later a window of 30
	minutes is allowed. The exact time of bleeding will anyway be registered on the log.
b	Pre infusion, 0.5hr, 1hr,2hr and 4hr (post-infusion)
	These samples will be collected 24 hours (range 18-36 hours) after completion of
	administration of the FOURTH dose of DTP3.
c	Further samples will be collected if a complete response is suspected or clinically required
	as determined by the Investigator
d	Patients receiving DTP3 after cycle 3 will continue with the assessments scheduled as per
-	cycle 3
	Dose Escalation Stage:
	Week 1 and 2: During Cycle 1, BP, pulse rate and 12 lead ECG will be carried out 15 min
	before and 30 mins, 60 min and 120 min after end of each DTP3 infusion (+/- 5mins).
	Week 3 and 4. During Cycle 1, BP, pulse rate and 12 lead ECG will be carried out 15 min before and 30 mins after end of each DTP3 infusion (+/- 5mins).
	Cycle 2-onwards : BP, pulse rate and 12 lead ECG will be carried out 15 min before and 30
	mins after end of each DTP3 infusion (+/- 5mins).
e	Cohort Expansion Stage:
	Week 1: During Cycle 1, BP, pulse rate and 12 lead ECG will be carried out 15 min before
	and 30 mins, after end of each DTP3 infusion.
	Week 2 onwards : BP, pulse rate and 12 lead ECG will be carried out before the first dose
	of DTP3 at the beginning of week 2 onwards (eg. before dose 4,7,10 etc)
f	Only to be done on a monthly basis in patients with detectable urinary M protein at
	screening
g	Pre-infusion
h	Bone marrow aspirate and biopsy required if radiological complete response
-	Serum pregnancy test (where appropriate) at beginning of each cycle of DTP3 and then
i	monthly for six months after cessation of DTP3 therapy.
j	To continue 8 weekly for evaluation as long as participating
	Where this is no Disease Progression when ceasing DTP3 treatment, survival status to
	continue being recorded for a period of six months after the last patient has been
k	recruited into the study. Via clinic team if under their care, or six weekly via family
	member.
1	Possible tests pending patient outcome of disease progression or complete resolution and
	local institutional practice:
	If at any point, a complete reponse is suspected in a patient, they will undergo:
	MM:
	 Two independent measurements (according to normal institutional practice)
	confirming:
	-negative immunofixation serum
	 -negative immunofixation urine 2. Bone marrow aspirate and biopsy (if above tests are consistent with definition of
	complete response)
	DIBCL:
	A bone marrow aspirate and biopsy is required for confirmation of radiological complete
	response.
	If at any point, there is clinical suspicion of disease progression :
	MM:
	This can be determined by measurement of any relevant disease parameter, including
	radiological imaging and/or bone marrow plasma cell percentage, but should be
	confirmed by two independent measurements, according to normal institutional practice.
	DLBCL:
	FDG-PET/CT imaging will be performed every 8 WEEKS after the first dose of DTP3, unless
	clinically indicated at an earlier time point (e.g. if there is clinical suspicion of disease
	progression). Response assessment at each FDG-PET/CT timepoint will be made according to the lugage 2014 orthogic (Appendix B of protocol).
	to the Lugano 2014 criteria (Appendix B of protocol).
	The most recently available weight should be used when calculating the amount of DTP3.
m	The weight used to calculate the dose of DTP3 can have been taken up to 10 days prior to
	administration of the first dose of each cycle)

Г

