2. STUDY OBJECTIVES AND ENDPOINTS

Objectives

Primary Objectives

- To select an optimal dose of DTP3 for further clinical evaluation [Recommended Phase 2 Dose (RP2D)] in patients with relapsed or refractory multiple myeloma or diffuse large B-cell lymphoma
- To assess the preliminary clinical efficacy of DTP3 in patients with relapsed or refractory multiple myeloma or diffuse large b-cell lymphoma

Secondary Objectives

- To assess the Dose Limiting Toxicity (DLT) and Maximum Tolerated Dose (MTD) of DTP3
- To assess the safety and tolerability of DTP3 in patients with relapsed or refractory multiple myeloma or diffuse large B-cell lymphoma
- To assess the pharmacokinetics of DTP3 in patients with relapsed or refractory multiple myeloma or diffuse large B-cell lymphoma
- To assess the pharmacodynamic activity of DTP3 in patients with relapsed or refractory multiple myeloma or diffuse large B-cell lymphoma
- To correlate GADD45β expression with pharmacodynamic and clinical response in patients with relapsed or refractory multiple myeloma or diffuse large B-cell lymphoma

Endpoints

Primary Endpoints

- Incidence, nature, and severity of all AEs, SAEs and DLTs
- Overall Response Rate (ORR)
 - **MM**: best overall response of stringent complete response (sCR), complete response CR, very good partial response (VGPR) or partial response (PR)
 - **DLBCL**: best overall response of PR or CR

Secondary Endpoints

- Changes in laboratory parameters, ECGs, vital signs
- Extent of exposure to DTP3
- PK parameters
- PD biomarkers of pathway-specific response:
- Correlation of GADD45¹ expression with pharmacodynamic and clinical response
- Relative reduction in levels of M protein and free light chains [MM only]
- Clinical Benefit Rate
 - MM: minimal response (MR) or better
 - **DLBCL**: CR plus PR plus stable disease (SD)

- Time to Response TTR)
- Duration of Response (DOR)
- Progression Free Survival (PFS)
- Event Free Survival [time to death, disease progression or initiation of non-protocol anti-cancer therapy] (EFS)
- Overall Survival (OS)

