7.5.2 DLBCL

FDG-PET/CT imaging will be performed every 8 WEEKS after the first dose of DTP3, unless clinically indicated at an earlier time point (*e.g.* if there is clinical suspicion of disease progression).

A bone marrow aspirate and biopsy is required for confirmation of radiological complete response in patients who had a positive bone marrow aspirate/biopsy at screening.

Response assessment at each FDG-PET/CT timepoint will be made according to the Lugano 2014 criteria (Appendix B).

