APPENDIX B: International Working Group Response Criteria for DLBCL (Lugano criteria)

Response and Site	PET-CT-based response	CT-based response
Complete	Complete Metabolic Response	Complete radiological response
Lymph nodes and extra-lymphatic sites	Score 1, 2, or 3* with or without a residual mass on 5PS ⁺ It is recognized that in Waldeyer's ring or extranodal sites with high physiologic uptake or with activation within spleen or marrow (eg, with chemotherapy or myeloid colony-stimulating factors), uptake may be greater than normal mediastinum and/or liver. In this circumstance, complete metabolic response may be inferred if uptake at sites of initial involvement is no greater than surrounding normal tissue even if the tissue has high physiologic uptake	All of the following Target nodes/nodal masses must regress to ≤ 1.5 cm in LDi No extra-lymphatic sites of disease
Non-measured lesion Organ enlargement New lesions Bone marrow	Not applicable Not applicable None No evidence of FDG-avid disease in marrow	Absent Regress to normal None Normal by morphology, if indeterminate, IHC negative
Partial	Partial metabolic response	Partial remission
Lymph nodes and extra-lymphatic sites	Score 4 or 5 ⁺ with reduced uptake compared with baseline and residual mass(es) of any size At interim, these findings suggest responding disease At end of treatment, these findings indicate residual disease	All of the following: ≤50% decrease in SPD of up to 6 target measurable nodes and extra-nodal sites When a lesion is too small to measure on CT, assign 5 mm x 5 mm as the default value When no longer visible, 0 x 0 mm For a node > 5 mm x 5 mm, but smaller than normal, use actual measurement for calculation
Non-measured lesion Organ enlargement	Not applicable Not applicable	Absent/normal, regressed, but no increase Spleen must have regressed by >50% in length beyond normal
New lesions Bone marrow	None Residual uptake higher than uptake in normal marrow but reduced compared with baseline (diffuse uptake compatible with reactive changes from chemotherapy allowed). If there are persistent focal changes in the marrow in the context of a nodal response, consideration should be given to further evaluation with MRI or biopsy or an interval scan	None Not applicable
No response or stable disease	No metabolic response	Stable disease

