Target nodes/nodal masses, extra-nodal lesions	Score 4 or 5 with no significant change in FDG uptake from baseline at interim or end of treatment	< 50% decrease from baseline in SPD of up to 6 dominant, measurable nodes and extra-nodal sites; no criteria for progressive disease are met
Non-measured lesions Organ enlargement New lesions	Not applicable Not applicable None	No increase consistent with progression No increase consistent with progression None

Bone marrow	No change from baseline	Not applicable
Progressive disease	Progressive metabolic disease	Progressive disease
Individual target	Score 4 or 5 with an increase in intensity of	All of the following:
nodes/nodal masses	uptake from baseline and/or	PPD progression:
Extra-nodal lesions	New FDG-avid foci consistent with lymphoma at	An individual node/lesion must be
	interim or end-of-treatment assessment	abnormal with:
		LDi >1.5 cm and Increase by ≥50% from
		PPD nadir and
		An increase in LDi or SDi from nadir
		0.5 cm for lesions \leq 2 cm
		1.0 cm for lesions >2 cm
		In the setting of splenomegaly, the splenic
		length must increase by > 50% of the
		extent of its prior increase beyond baseline
		(eg, a 15-cm spleen must increase to >16
		cm). If no prior splenomegaly, must
		increase by at least 2 cm from baseline.
		New or recurrent splenomegaly
Non-measured lesions	None	New or clear progression of pre-existing non-measured lesions
New lesions	New FDG-avid foci consistent with lymphoma	Regrowth of previously resolved lesions
	rather than another etiology (eg, infection,	A new node >1.5 cm in any axis
	inflammation). If uncertain regarding etiology of	A new extra-nodal site >1.0 cm in any axis;
	new lesions, biopsy or interval scan may be	if < 1.0 cm in any axis, its presence must be
	considered	unequivocal and must be attributable to
		lymphoma.
		Assessable disease of any size
		unequivocally attributable to lymphoma
Bone marrow	New or recurrent FDG-avid foci	New or recurrent involvement

Abbreviations: 5PS, 5-point scale; CT, computed tomography; FDG, fluorodeoxyglucose; IHC, immunohistochemistry; LDi, longest transverse diameter of a lesion; MRI, magnetic resonance imaging; PET, positron emission tomography; PPD, cross product of the LDi and perpendicular diameter; SDi, shortest axis perpendicular to the LDi; SPD, sum of the product of the perpendicular diameters for multiple lesions.

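### Appendix B's CT threshold for partial response contradicts its own stable-disease row, and the protocol does not say which imaging column decides DLBCL response

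*Protocol*

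**What the plan says.** Section 2 makes overall response rate a primary endpoint, defined for DLBCL as "best overall response of PR or CR". Section 7.5.2 schedules FDG-PET/CT every 8 weeks and states: "Response assessment at each FDG-PET/CT timepoint will be made according to the Lugano 2014 criteria (Appendix B".

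Appendix B sets out two parallel columns, one PET-CT-based and one CT-based. The relevant cells are:

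- **CT, partial remission, nodes and extra-nodal sites:** "≤50% decrease in SPD of up to 6 target measurable nodes and extra-nodal sites" (SPD is the sum of the products of the perpendicular diameters).
- **CT, partial remission, spleen:** "Spleen must have regressed by >50% in length beyond normal".
- **CT, stable disease:** "< 50% decrease from baseline in SPD of up to 6 dominant, measurable nodes and extra-nodal sites", with no progression criteria met.
- **PET-CT, partial metabolic response:** score 4 or 5 "with reduced uptake compared with baseline and residual mass(es) of any size".
- **CT, progressive disease, target lesions:** a heading that requires all listed items, followed by nodal growth, splenic enlargement and "New or recurrent splenomegaly" in one cell.

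Section 8.1 sets the decision rule: 24 patients per cohort, an exact one-sided 90% lower limit, and a minimum response rate of 25%.

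**The concern.** The CT partial-remission cell has its inequality the wrong way round relative to the row below it. A category meant to capture substantial shrinkage is written as shrinkage of at most 50%, and this overlaps almost completely with stable disease. Partial response is one of the two components of the DLBCL primary endpoint, so a reader who applied the CT column literally would have no consistent rule for separating response from non-response.

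The protocol does not keep the CT column clearly out of use. Section 7.5.2 refers to Appendix B as a whole. The same section asks for marrow confirmation of a complete response that it calls radiological, which is the CT column's term; the PET-CT column says metabolic. The clinical benefit rate counts "CR plus PR plus stable disease (SD", and stable disease is the CT column's name for what the PET-CT column calls no metabolic response. Inclusion criterion 11 (section 4.2.1) requires lesions measured in two axes on CT or MRI, so a reader would have the baseline dimensions from which to compute SPD.

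**Working it through.** **Step 1: the plan's own figure.** Inputs from section 8.1: n = 24, observed rate 41.7% (10/24), exact Clopper-Pearson, one-sided 90%. The lower limit for r responses is the 0.10 quantile of a Beta(r, n − r + 1) distribution. For r = 10 this is Beta(10, 15), which gives 27.72% and reproduces the stated 27.7%. The lower end of a two-sided 90% interval would be 24.64%, so the one-sided reading is the one used.

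**Step 2: classify SPD changes under the printed rows.** This looks at the SPD condition alone.

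| SPD decrease | Printed PR (at most 50%) | Printed SD (below 50%) | If PR were 50% or more |
|---|---|---|---|
| 0%, 10%, 30%, 49.9% | met | met | SD only |
| 50% | met | not met | PR only |
| 50.1%, 60%, 80% | not met | not met | PR only |

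The printed rows overlap everywhere below 50% and leave a gap everywhere above it. Reversing the sign removes both faults. A CT partial response also requires no new lesions, no increase in non-measured lesions and the spleen criterion, so meeting the SPD condition does not by itself make a patient a responder.

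**Step 3: which direction was intended.** Three places in the protocol agree. The stable-disease row leaves 50% or more as its only complement. The spleen item for partial remission in the same column asks for regression of more than 50%. Appendix A asks for at least a 50% reduction in SPD of plasmacytomas for partial response in myeloma.

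**Step 4: how close the decision is.** One patient is 1/24 = 4.2 percentage points.

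| Responses | Observed rate | Exact one-sided 90% lower limit | Above 25%? |
|---|---|---|---|
| 8/24 | 33.3% | 20.5% | no |
| 9/24 | 37.5% | 24.1% | no |
| 10/24 | 41.7% | 27.7% | yes |
| 11/24 | 45.8% | 31.5% | yes |

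One stable patient scored as a responder (9 to 10) crosses the line upwards. One true responder lost (10 to 9) crosses it downwards.

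**Step 5: illustration in one direction only.** Assume a true response rate p = 25% and a share m of non-responders counted as partial responses through the CT row. Neither value comes from the protocol. The apparent rate is q = p + m(1 − p), and the chance of at least 10/24 is the binomial upper tail at q.

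- m = 0: q = 25%, chance 5.5%
- m = 5%: q = 0.25 + 0.05 × 0.75 = 28.75%, chance 12.2%
- m = 10%: q = 0.25 + 0.10 × 0.75 = 32.5%, chance 22.6%
- m = 20%: q = 0.25 + 0.20 × 0.75 = 40%, chance 51.1%

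This ignores responders lost through the gap above 50%, which would pull the other way.

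**The case against.** The strongest reply is that the faulty column is not the scheduled modality. FDG-PET/CT is done every 8 weeks, inclusion criterion 11 requires PET-positive lesions at baseline, and the PET-CT column defines partial response by uptake whatever the residual size. With PET available throughout, the column headings themselves point to the unaffected column. The slip is also easy to recognise against the stable-disease row, and the protocol names Lugano 2014 as its criteria. This limits how often the error can matter, and it stands. It does not remove the error, because no sentence says that the PET-CT column prevails or what happens when PET is missing.

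A reader might infer three stronger things that the protocol does not support:

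- **That the error inflates the response rate.** The printed rule errs both ways, so the net direction is unknown. A shift such as 8/24 to 10/24 (20.5% to 27.7%) would be hypothetical; nothing in the protocol indicates how many patients would be misclassified.
- **That a patient without splenic disease could never progress on CT.** Under progressive disease, Appendix B has separate CT rows for new lesions, non-measured lesions and bone marrow, and the first splenic item applies only where there is splenomegaly. What remains is an ambiguous target-lesion cell.
- **That the sign might be a fault of text extraction.** Neighbouring inequality signs in the table read sensibly, so this is unlikely, but the source PDF should be checked.

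**Conclusion.** The CT partial-remission cell contradicts the CT stable-disease row and runs opposite to the spleen criterion in its own column. This is shown by Appendix B alone. It is more than a slip in background text, because section 7.5.2 makes the appendix the operative definition for a primary endpoint and no rule says which column governs.

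The consequence is conditional. It arises only where the CT column decides a response and the other CT conditions are also met. The number of such patients cannot be derived from the protocol and may be small. The error could add non-responders or lose responders. It deserves correction before DLBCL responses are analysed because the decision margin is a single patient: 24.1% at 9/24 and 27.7% at 10/24, against 25%. Those limits assume a denominator of exactly 24. The sample size and the stated 27.7% do not depend on the threshold, and the myeloma cohort is unaffected.

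Separately, the CT target-lesion progression cell is ambiguous, because it lists nodal and splenic items together under a heading that requires all of them.

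**What to change.** 1. Check the sign in the source PDF, then correct the CT partial-remission cell to a decrease of 50% or more, so that it complements the stable-disease row.
2. State in section 7.5.2 and Appendix B that the PET-CT column determines DLBCL overall response rate, and that the CT column is used only where PET is missing or not evaluable. Align the term used for complete response in section 7.5.2 with that choice.
3. Recheck any DLBCL response already scored on the CT column, looking both for stable patients counted as responders and for responders left unclassified.
4. Reconcile the wording of the CT target-lesion progression cell. Section 5 ties the end of treatment to progression as defined in this appendix, so how the items combine is for the sponsor and investigators to settle. New lesions, non-measured lesions and marrow already have their own rows.

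The cost is a corrected appendix table, a sentence on which column governs, a note to site readers and a review of any CT-scored cases. The sample size does not change.

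### In Appendix B, the CT-based partial-remission threshold for DLBCL is printed with its sign apparently reversed and contradicts the stable-disease row, and section 7.5.2 does not say whether the CT or the PET-CT column governs

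*Protocol*

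**What the plan says.** Section 2 defines the primary DLBCL efficacy endpoint, overall response rate (ORR), as "best overall response of PR or CR". Stable disease counts only towards the secondary Clinical Benefit Rate, which adds it to CR and PR.

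Section 7.5.2 schedules FDG-PET/CT every 8 weeks and fixes the response rule: "Response assessment at each FDG-PET/CT timepoint will be made according to the Lugano 2014 criteria (Appendix B"). It does not name a column of that appendix.

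Appendix B has two columns, one PET-CT-based and one CT-based. The nodal entries that matter here are:

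- CT-based complete response: "Target nodes/nodal masses must regress to ≤ 1.5 cm in LDi", with no extra-lymphatic disease.
- CT-based partial remission: "≤50% decrease in SPD of up to 6 target measurable nodes and extra-nodal sites".
- CT-based stable disease: "< 50% decrease from baseline in SPD of up to 6 dominant, measurable nodes and extra-nodal sites; no criteria for progressive disease are met".
- CT-based partial remission, spleen: "Spleen must have regressed by >50% in length beyond normal".
- PET-CT-based partial response: a score of 4 or 5 "with reduced uptake compared with baseline and residual mass(es) of any size", with no SPD threshold.

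Section 8.1 sets the bar for the expansion cohort. With 24 patients and an observed rate of at least 41.7%, the one-sided 90% exact lower limit is at least 27.7%, which exceeds the 25% minimum.

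**The concern.** Partial remission and stable disease should divide the range of shrinkage between them. In the CT column they do not: both criteria are upper bounds on the decrease, so they overlap over nearly the whole range below 50% and leave the range above 50% to complete response alone.

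The boundary between these two categories decides who is a responder. Where an assessor works from the CT column, a patient with minor shrinkage can be read as a responder or as stable. A patient with large shrinkage short of CR has no category. Time to response and duration of response use the same definition of PR. With 24 patients per cohort, reclassifying a single patient can move the lower limit across 25%.

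**Working it through.** **1. The plan's own figure.** Inputs from section 8.1: n = 24, observed rate 41.7% (r = 10, since 10/24 = 0.4167), one-sided 90% Clopper-Pearson limit. The lower limit is the 0.10 quantile of a Beta(r, n − r + 1) distribution.

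- r = 10: Beta(10, 15), 0.10 quantile = 0.2772, or 27.7%. This reproduces the stated figure.
- r = 9: Beta(9, 16), 0.10 quantile = 0.2406, or 24.1%, which is below 25%.

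Ten responders of 24 is therefore the smallest count that clears the 25% minimum, and the tenth responder decides it.

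**2. The two CT nodal criteria, value by value.** The partial-remission cell is tested as printed (decrease ≤ 50%) and with the sign turned (decrease ≥ 50%), each against stable disease (decrease < 50%).

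| Decrease in SPD | PR as printed | SD | PR with sign turned |
|---|---|---|---|
| 0% | yes | yes | no |
| 10% | yes | yes | no |
| 30% | yes | yes | no |
| 49% | yes | yes | no |
| 50% | yes | no | yes |
| 51% | no | no | yes |
| 70% | no | no | yes |
| 90% | no | no | yes |

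As printed, only a decrease of exactly 50% falls into one and only one of the two categories. With the sign turned, every value does.

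**3. Which cell is wrong.** The table settles this without the cited source. The spleen item in the same partial-remission category requires regression of more than 50%, which is a lower bound. The stable-disease cell is coherent as the complement of a lower bound at 50%. The nodal partial-remission cell is the only one out of line.

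**4. What it does to the endpoints if the CT column is applied, on the nodal criterion alone.**

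- Decrease below 50%: ORR is ambiguous, because the patient meets PR and SD. The Clinical Benefit Rate is unchanged, because both categories count.
- Decrease above 50%, short of CT complete response: the patient is neither PR nor SD, so is lost from both ORR and the Clinical Benefit Rate.

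ORR can therefore be pushed up by the first group and down by the second. The Clinical Benefit Rate can only lose patients.

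**5. How often the CT column is applied.** The documents give no figure. On-study imaging is by FDG-PET/CT, and inclusion criterion 11 requires PET-positive disease at baseline, so the share may be zero. It is not excluded, because no section assigns precedence to the PET-CT column.

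**The case against.** The strongest case against is that the faulty column is not the one the schedule calls for. DLBCL response is imaged only by FDG-PET/CT, in patients who were PET-positive at entry, and the PET-CT column contains no error. Nothing in the protocol directs a CT-only assessment. The criteria are also fixed by name to Lugano 2014 in several sections, and an assessor who finds a 30% decrease in two categories and a 70% decrease in none would probably recognise a slip. This stands as a limit on the effect.

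It does not clear the text. Section 7.5.2 makes the whole appendix the rule, and its marrow requirement is tied to a radiological complete response. That is the CT column's term; the PET-CT column speaks of a metabolic one. Measurable disease at entry is also defined by CT or MRI dimensions.

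A second objection is that the point rests on one machine-read character. The same table shows both ≤ and ≥ sensibly elsewhere, so a reading error is unlikely, but the original page should be checked.

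Three stronger readings are tempting and are not supported:

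- A reader might infer that stable disease will be counted as response in the primary ORR. That follows only where the CT column is applied.
- A reader might infer that all larger shrinkage is unclassifiable. CT complete response can still take it; the gap is a decrease above 50% short of CR.
- A reader might try to size an inflated ORR by adding patients with minor shrinkage to an assumed true response rate. That keeps the true partial responders above 50%, whom the literal wording drops, so it joins two incompatible readings. The documents also supply neither input.

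**Conclusion.** The CT-based partial-remission cell is wrong as written, since it contradicts the stable-disease row of its own column and runs opposite to the spleen item of its own category. The effect on the primary DLBCL ORR and the Clinical Benefit Rate is conditional on use of the CT column. That share is not given and may be nil, so neither the size nor, for ORR, the direction of the effect can be stated. What can be stated is the sensitivity: with exactly 24 patients, 9 responders give a lower limit of 24.1% and 10 give 27.7%, on either side of the 25% minimum. The conclusion assumes that the printed page carries the same sign as the text read here. This is a should-fix correction rather than a must-fix, because the scheduled assessment has its own, correct column.

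**What to change.** 1. Check the sign on the original page of Appendix B.
2. Change the nodal criterion for CT-based partial remission to a decrease in SPD of at least 50% (≥ 50%), so that it complements the stable-disease cell.
3. State in section 7.5.2 that the PET-CT column governs response, and in which circumstances, if any, the CT column may be used.
4. Notify sites, and re-check any DLBCL response that was recorded on the CT column. If there is none, record that.

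The cost is one character in the appendix, one or two sentences in section 7.5.2 and a site notification. No new assessments are needed, and the sample-size statement in section 8.1 is unchanged.
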